9.4 Passive collection of incidence data

Incidence data from each locality will be collected passively for the entire study period starting from the first incident case reported in that locality. As this data will be de-identified and is part of standard surveillance, IRB approval will not be necessary for this data collection. Incidence data will be collected as: incidence of local cases (not counting the first case), proportion of imported cases (a surrogate measure of R_c [27]), and time to first end-line local incident case.

10 Acceptability Assessment

10.1 Background and Rationale

For the quantitative portion of the Acceptability Assessment, acceptability of TPE versus RACD will be evaluated by comparing refusal rates and analyzing answers from a short survey.

This qualitative portion of the Acceptability Assessment proposes to explore the acceptability of TPE from two vantage points; 1) among study participants and participants and 2) among members of the RACD and TPE surveillance teams. We will target only members of the TPE arm for acceptability assessment since RACD is the current standard in this setting and acceptability has been high. Additionally, the surveillance team will participate in qualitative exercises to enhance understanding of acceptance and refusal during the study given their constant exposure to community members offered the interventions. The results of the Acceptability Assessment will be used to refine strategies for malaria elimination in Swaziland and other malaria-eliminating settings.

We will use focus group discussions (FGDs) to understand participants' situational perspective in regard to the clinical trial [28]. The importance of using qualitative methods as an adjunct to clinical trials has been documented [29]. Additionally, this approach has been validated, as previous studies have successfully used FGDs to capture important information regarding community acceptability of new treatment modalities [30, 31]. All data will be collected by members of the field surveillance team who are native SiSwati speakers.

We will conduct the Acceptability Assessment with community participants approximately 7-10 days after an intervention (during the follow-up pill count) has occurred in a TPE community with a positive malaria case. We anticipate enrolling participants in the TPE arm for the duration of the study. We will conduct the acceptability assessment with the malaria surveillance team every 3 months for the duration of the study, beginning 3 months after the study launch.

10.2 Aims of the Acceptability Assessment

Aim 1: To compare refusal rates between the RACD and TPE arms. A short survey of those who refuse testing or treatment will be administered at the time of refusal. The short survey of refusers will ask questions about past participation in malaria screening and reasons for refusing participation in this clinical trial.

Aim 2: To understand reasons for adherence among TPE study participants receiving treatment without testing.

To appreciate the reasons for accepting TPE, we will identify study participants to explore acceptability of both practices. Methods will entail FGDs with community members who have agreed to participate in the clinical trial. The FGDs will explore past experience with malaria testing, impact of testing or treatment on daily life, and beliefs surrounding malaria transmission and possible elimination.

Aim 3: To explore the surveillance team's perception of community acceptance of RACD versus TPE.

During the clinical trial to compare RACD versus TPE around positive malaria index cases, the field surveillance team interacts with the community members to facilitate the study. Using FGDs, we will explore the acceptability of both arms of the clinical trial from the vantage point of these field surveillance team members. FGDs will be used to explore their experience consenting participants for the study and reasons community members agree or disagree to receive testing and/or treatment.

10.3 Methods for the Acceptability Assessment

Aim 1:

At the time of refusal, we will ask all community members who refuse participation in either study arm to answer a short survey. The survey will be administered by the surveillance team member on site and uploaded to an excel spreadsheet during the study. These surveys will be anonymous and take approximately 5-10 minutes. Questions include but are not limited to: "Have you ever refused to take part in a malaria screening in the past?" "If yes, why did you refuse?" "Has anything in the past with medication influenced your decision not to participate in the intervention?" (Appendix V). Participation will be completely voluntary and all refuser information will be de-identified before analysis. Information from the short survey will be evaluated during the study so that information may be used to inform the study team activities. Information from the refuser survey will be aggregated and reviewed by the study team to identify any apparent reasons for refusals.

Aim 2:

From each TPE study locality, we will ask participants if they agree to be part of a group discussion 7-10 days after the intervention (at the pill count follow up visit). From those we will choose 3-7 study participants at each site to form a focus group. As we intend to conduct a FGD in all TPE study localities beginning at the study launch, we anticipate a total of 30 FGDs during the course of the study. FGDs will be conducted 7-10 days after the TPE intervention; therefore data collection will take place on a rolling basis throughout the study. Our intent is to capture information for the duration of the study and begin analysis with the first focus group. We will evaluate changes in community uptake over time by using an iterative approach to analysis.

The goal of Aim 2 is to understand why TPE community members agree to participate in interventions around a malaria index case. FGDs will be audio-recorded and the interviewers will take notes during the sessions. Interviewers will consist of two members of the field surveillance team who are native siSwati speakers. All FGDs will take place in the village where the participants reside and be audio-recorded with written consent from the study participant. FGDs will last an estimated 1 hour and we will inquire about the participants' experience with the interventions, their personal history of malaria, their experience with testing and treatment and the impact of these interventions on daily life. Sample questions include but are not limited to: "Have you ever been part of the NMCPs screening for malaria in affected communities?" "How was your experience with the screening test done by the NMCP officers?" "What do you think about getting tested for malaria before you take medication? Is it important? Why or why not?" "How did the medication make you feel after taking it?" (Appendix W). Afterwards, the audio-recordings will be translated, transcribed and a brief summary will be written for each interview. We will upload and code the FGDs transcripts using an analytical software program, ATLAS.ti5, with the assistance of the study team. Major themes will be identified by two members of the study team independently. Any discrepancies will be resolved by inviting a 3rd member of the study team to verify findings. Data will then be analyzed to provide a description of the barriers and facilitators to participation in TPE. The themes that emerge will enable us to design future interventions to improve elimination strategies.

Aim 3:

Qualitative methods described in Aim 2 will be employed in Aim 3. However, the goal of Aim 3 is to explore how members of the study surveillance team (who interact with community members enrolled in both the RACD and TPE arms) perceive community acceptance of the interventions (Appendix X). We will conduct FGDs with the entire surveillance team every 3 months, beginning 3 months after the study launch and continue for the duration of the study. FGDs will be conducted in siSwati and led by a member outside the surveillance group who is indirectly involved in the study. All participants will provide written informed consent prior to the conduct of interviews. The FGDs will be semi-structured and will focus on the observations of these surveillance team members during the study. Specifically, we will focus on their experience consenting participants for both intervention arms, reasons community members gave for accepting or refusing participation, experience with DOT and their perceptions of how to engage community members in malaria elimination strategies. The FGDs will last an estimated 1 hour. All interviews will be audio-recorded with written consent from the participants, then transcribed and uploaded to Atlas.ti for management and analysis. Participants will be assured that their responses will not impact their position on the surveillance team. Data will then be analyzed to identify major themes associated with the acceptance of malaria elimination strategies by both community members and surveillance team members. Ultimately, we will describe facilitators and barriers to these strategies with the goal of identifying the most acceptable way to engage the community in malaria elimination.

Table 5. Acceptability Assessment – Study population, sample size, inclusion and exclusion criteria

Aim	Study population and sample size	Inclusion criteria for Acceptability Assessment	Exclusion criteria for the Acceptability Assessment
1: Refusers	All eligible residents of the TPE arm who refuse participation	
 • Male and female refusers at time of study intervention • Agrees to a short anonymous survey 	
 • Resides in RACD study locality • Age <18 years • Refusal to participate in the refuser survey
2: FGDs with TPE study participants	Non-index cases residing within TPE study localities, 3-7 participants per FGD, anticipate 30 TPE study localities over duration of study.	
 • Male and female participants • Residents of index household • Residents of neighboring households • Provide informed consent (participants) 	
 • Resides in RACD study locality • Refusal to participate in the Acceptability Assessment • Speaks language not understood or able to be translated to interviewer. • Age < 18 years
3: FGDs with TPE & RACD surveillance team members	All members of the surveillance team in both TPE & RACD study arms	
 • Provide informed consent 	
 • Refusal to participate

11 Cost-effectiveness assessment

The goal of the cost effectiveness assessment will be compare TPE versus RACD in terms of costs per response or incident case of as well as cost per population and case averted as measured through the difference in asymptomatic and symptomatic infections identified at the end of the intervention. Our hypothesis is that the costs of TPE versus RACD will be lower due to the cost savings from not performing a diagnostic test as well as the cases averted due to higher effectiveness to prevent future infections.

We will collect detailed expenditure data on costs of delivery of TPE and RACD interventions. Calculations will include costs for all consumables as well as staff time, which will be prospectively collected every 10th TPE or RACD event.

12 Laboratory procedures

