The sample size for the Target Area assessments is estimated from incidence in the previous transmission season, and the expected drop in incidence among those in the TPE arm; resulting in an estimated 200 index cases total with 30 individuals screened or treated in the Target Areas around each case. With 200 index cases, we expect about 6000 encounters where individuals will receive a study intervention (either TPE or RACD). Based on preliminary RACD data, we anticipate 10% of these encounters will occur in individuals who previously received an intervention during the study period (repeated or overlapping Target Areas). For the follow-up end-line seroprevalence survey, these individuals will only be sampled once. Thus the effective sample size for the seroprevalence outcome measured in the Target Area population is expected to be 5400. Of note, the first index case for each Target Area will not be included since this person's malaria exposure occurred pre-intervention.

For the follow-up end-line infection prevalence survey, index cases will also be included as they will also be at risk for subsequent infection. Thus the effective sample size for the infection prevalence outcome measured in the Target Area population will be 5400 individuals screened plus 200 index cases, or 5600 individuals.

Adherence evaluation:

Adherence will be measured on a subsample that includes only the individuals in the Target Areas surrounding the first index case in each locality. We expect that 22 localities in the TPE arm will have at least one index case, and at least 30 individuals will be assessed for DP treatment per Target Area, for a total sample of 660 individuals.

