End-line seroprevalence for RACD was calculated based on an estimate that only 20% of individuals with infection will be detected by RACD and treated, leading to a 20% effectiveness of RACD, or a drop from 3.0% pre-intervention to 2.4% end-line seroprevalence. We believe that TPE will be more effective than RACD in reducing seroprevalence near the end of the study (expected mid 2017). Because of the clustered nature of the data and the variability in cluster size, we used the harmonic mean number of observations expected per locality (60) to generate the effective sample size for analytic power (3780). Using these assumptions, our study would have 80% power to detect a decrease in seroprevalence to 1.18% in the TPE arm if 63 of the 77 localities had at least one case (Table 8).

Secondary outcome on feasibility – Coverage:

For the feasibility outcome measure on coverage, estimates were based on the goal TPE coverage of 80%. This goal is based on modeling data which suggests at least 80% coverage is needed for MDA to be successful, as well as experience from some settings that have successfully interrupted transmission in the setting of MDA [8, 18]. If estimates of incidence in the TPE arm are accurate, approximately 66 index cases will be identified and 1782 individuals will be treated in the TPE-assigned Target Areas. If the true coverage is 80% coverage, we would have a 95% confidence interval between 77% and 83% with this sample size [38].

Secondary outcome on feasibility – Adherence:

To measure adherence to DP, we will perform a pill count in individuals residing in the first Target Area for each TPE locality each transmission season. We will have 5% absolute precision to detect 80% adherence when the sample size reaches 532. If adherence is lower than expected, we will still have 10% absolute precision to detect 50% adherence when the sample size 208.

Table 7. Detectable Reductions in cumulative incidence given different assumptions about Incidence in the RACD

# Total localities with at least one index case	# localities per arm	Number assessed per locality (n)		Cumulative Incidence		Km (coeff of variation)	Z beta	Power
		RACD	TPE	RACD (π_0)	TPE(π_1)			
47.0	23.5	656	656	0.500%	0.250%	0.9	0.84	80%
50.6	25.3	656	656	0.400%	0.200%	0.9	0.84	80%
56.6	28.3	656	656	0.300%	0.150%	0.9	0.84	80%
61.4	30.7	656	656	0.250%	0.125%	0.9	0.84	80%
68.5	34.3	656	656	0.200%	0.100%	0.9	0.84	80%
80.5	40.2	656	656	0.150%	0.075%	0.9	0.84	80%

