Based on equation 4 from Hayes and Bennett International Journal of Epidemiology 1999;28:319-32

Assumes that population is only those in the EAs that have at least one case.

Sample size calculation based on harmonic mean of population size.

Table 8. Detectable reductions in seroprevalence given varying assumptions about prevalence in the RACD arm

# Total localities with at least one index case	# localities per arm	Number assessed per locality (n)		Outcome proportion		Km (coeff of variation)	Z beta	Power
		RACD	TPE	RACD (π_0)	TPE (π_1)			
46.6	23.3	60	60	3.00%	1.35%	0.9	0.84	80%
62.3	31.2	60	60	2.40%	1.18%	0.9	0.84	80%
49.3	24.7	60	60	2.00%	0.83%	0.9	0.84	80%
50.8	25.4	60	60	1.50%	0.57%	0.9	0.84	80%

Based on equation 4 from Hayes and Bennett International Journal of Epidemiology 1999; 28:319-326

Assumes we are including only persons in the target areas in the denominator but evaluating at locality level

Assumes 3 per 100 is the background seroprevalence

Table 9. Sample sizes for primary and secondary aims.

Outcome	Result*	Actual sample size (Effective sample size, based on harmonic mean in clusters)
Primary aim		
Incidence	0.4% (RACD) vs. 0.2% (TPE)	55,928 (41,328)
Secondary aims (effectiveness)		
Exposure (seroprevalence)	2.4% (RACD) vs. 1.18% (TPE)	5400 not including index cases (3720)
Infection prevalence	n/a	5600 includes index cases
Time to first post-intervention incident case	n/a	55,928 (41,328)

Outcome	Result*	Actual sample size (Effective sample size, based on harmonic mean in clusters)
Proportion of imported incident cases	n/a	55,928 (41,328)
Transmission potential	n/a	Genotyping estimated to be performed in 800 index cases** and 35 infections from follow-up cross sectional survey
Secondary aims (feasibility)		
Coverage in TPE Arm	80% (95% CI: 77%-83%)	1782
Adherence in TPE Arm	80%	532
Prevalence of SAEs related to treatment	n/a	5400 not including index cases (3720)
Acceptability	n/a	5400 not including index cases (3720)
Cost	n/a	10 Target Areas/arm

*for some secondary outcomes, power calculations were not performed however effective sample size is shown.

** 200 index cases will be from the study area but an estimated 600 DBS that are already collected as standard surveillance from other parts of the country will also be used to characterize the background genotypes/transmission potential in Swaziland, as it relates to the transmission potential in the study areas.

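### Section 11 gives no denominator for cases averted, so the survey component can depend on how many people are sampled per arm; separately, costing every 10th event does not yield 10 events per arm

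*Combined protocol and SAP*

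**What the plan says.** Section 11 compares the arms on several cost measures. For cost per case averted, the effect is the "case averted as measured through the difference in asymptomatic and symptomatic infections identified at the end of the intervention". Table 6 lists cost per case averted as an outcome without a denominator. The cost item in Section 14.4 covers cost per incident infection and per population but does not mention cases averted.

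The asymptomatic infections would come from the end-line survey, which invites all residents of Target Areas (Section 9.3). Those areas are 200 m around the index case in TPE, extended if fewer than 30 people are enrolled, and 500 m in RACD (Section 4.4). Section 14.1 sizes the survey from past surveillance and already builds in a benefit of TPE, described as "and the expected drop in incidence among those in the TPE arm". It arrives at 200 index cases over both arms and 30 people per Target Area. It then says "we anticipate 10% of these encounters will occur in individuals who previously received an intervention during the study period" and concludes: "Thus the effective sample size for the seroprevalence outcome measured in the Target Area population is expected to be 5400". For the TPE arm, Section 14.3 expects that "approximately 66 index cases will be identified and 1782 individuals will be treated".

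On costing, Section 11 says that staff time and consumables enter the calculation, "which will be prospectively collected every 10th TPE or RACD event". The study summary gives the same interval. Table 9 gives the costing sample as "10 Target Areas/arm", and Section 14.4 repeats that number.

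**The concern.** A difference in infections found is a difference in effect only if the two arms search equally sized and comparable populations. If more people are surveyed in RACD, more infections are found there at the same prevalence. The shortfall in TPE would then be booked as infections averted, although those infections were simply not looked for. This enlarges the denominator of cost per case averted and makes TPE look cheaper per case.

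The costing sample raises a smaller question. A one-in-ten rule and a fixed 10 per arm agree only if each arm has about 100 events, and the plan does not expect that. The cost estimate for the new intervention would rest on fewer events than stated.

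**Working it through.** **Inputs.** 200 index cases, 30 people per Target Area and 10% repeat encounters (Section 14.1); 66 TPE index cases and 1,782 people (Section 14.3); about 134 index cases per study year (Section 4.4); RACD incidence 0.4% against TPE 0.2% (Table 9). Illustrative prevalences are 0.9% (LAMP positivity in past RACD, Section 1.3) and 0.4% and 1.6% (the two end-line values in the genotyping item of Section 14.4, used here only as a range).

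**Step 1: reproduce the plan's survey sizes.** People = index cases × 30 × 0.90.
- Total: 200 × 30 × 0.90 = 5,400, as stated.
- TPE: 66 × 30 × 0.90 = 1,782, as stated.
- RACD by subtraction: 200 − 66 = 134 index cases; 134 × 30 × 0.90 = 3,618 people.
- Ratio: 3,618 / 1,782 = 2.03.

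The RACD figures are derived here; the plan does not state the end-line sample by arm.

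**Step 2: where the 2:1 split comes from.** Two seasons at 134 per year give 268 index cases, or about 134 per arm if TPE has no effect. Halving one arm gives 134 + 67 = 201, which is the plan's 200. The split is therefore a consequence of the assumed 50% reduction.

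**Step 3: raw count at the design point, end-line prevalence equal in both arms.** Difference = (3,618 − 1,782) × prevalence.

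| Prevalence | RACD found | TPE found | Difference |
|---|---|---|---|
| 0.4% | 14.5 | 7.1 | 7.3 |
| 0.9% | 32.6 | 16.0 | 16.5 |
| 1.6% | 57.9 | 28.5 | 29.4 |

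A difference in proportions would be zero in every row. The reduction in index cases is already counted once, as roughly 134 − 66 = 68. The survey count adds 7.3/68 = 11%, 16.5/68 = 24% or 29.4/68 = 43% to it. For a given cost difference, cost per case averted falls by 1 − 68/75.3 = 10%, 1 − 68/84.5 = 20% or 1 − 68/97.4 = 30%.

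**Step 4: raw count with no effect.** With 134 index cases and 30 people per Target Area in each arm, both surveys have 3,618 people and the difference is zero. If RACD areas hold k times as many residents because of the wider radius, the difference is 3,618 × (k − 1) × prevalence. The documents do not give k. I take 1 to 6.25 as an assumption, the upper end being the area ratio (500/200)² at uniform density. At 0.9% this gives 0 for k = 1, 32.6 for k = 2 and 171 for k = 6.25. The last is an outer bound. Section 1.3 reports lower odds of infection at 201–500 m than within 100 m, and Section 4.4 reports a mean of only 32 people screened per index case.

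**Step 5: costing sample.** Events / 10, taking one event per index case.
- TPE: 66/10 = 6.6, so 6 or at most 7.
- RACD: 134/10 = 13.4, so 13.
- Equal split of the 200: 100/10 = 10 per arm, which is the stated figure.
- No effect: 134/10 = 13.4 in each arm.

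**The case against.** A reader might infer from the 2:1 survey size that TPE will be credited with averted infections even if it does nothing. The documents do not support that. The 66 TPE index cases are conditional on the assumed TPE incidence, and without an effect the same inputs give equal surveys. The 7, 16.5 and 29 apply only if TPE halves index cases but leaves Target Area prevalence unchanged. A no-effect bias can arise only through the different radii, and the plan's own sizing uses 30 people per area in both arms, which makes it zero.

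A reader might also infer that the plan has committed itself to raw counts. It has not. Table 6 defines incidence and prevalence as proportions, Section 14.4 models them with GEE, and Section 11 also lists cost per population. A rate difference is not excluded; it is just not specified.

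Two further objections stand. Symptomatic cases come from passive surveillance of 39 TPE and 38 RACD localities, so they do not depend on survey size. And the 1,782 is a count of people treated, given for the coverage calculation, whereas the survey also takes in non-participants and newcomers.

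On costing, the shortfall is conditional too: with 100 to 134 TPE events, every 10th gives 10 to 13. Table 9 attaches no precision to the cost outcome, so no stated power is lost.

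None of this supplies the missing denominator, and the two costing statements still disagree under the plan's own assumptions.

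**Conclusion.** The point holds as a gap in definition. Section 11 does not say on what population infections averted are counted, and its literal wording makes the asymptomatic component depend on survey size. At the design point, a raw count would add about 7, 16.5 or 29 infections at 0.4%, 0.9% or 1.6% prevalence. This rests on the derived split of 3,618 and 1,782 and on unchanged end-line prevalence. With no effect, the bias runs from zero upwards according to how many more people the 500 m areas hold, which the documents do not give.

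The costing mismatch holds on the plan's figures: about 6 to 7 TPE and 13 RACD events against 10 stated for each. The 10 follows only from an equal split of the 200 events.

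Both matters concern a secondary feasibility outcome and leave the primary analysis untouched. The priority is low.

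**What to change.** In Section 11 and Table 6, define cases averted as the sum of two parts: the incidence difference from the primary analysis, and the end-line prevalence difference, each applied to a stated population that is the same for both arms. Compare prevalence over the same radius, for example residents within 200 m of the index case. Otherwise the wider RACD areas bring in lower-risk residents, which would bias the prevalence difference against TPE. Give intervals that respect clustering by locality. Add the measure to the cost item in Section 14.4.

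For costing, either restate the expected sample in Table 9 and Section 14.4 as about 6 to 7 TPE and 13 RACD events (10 to 13 TPE if the effect is smaller than assumed), or keep a target of 10 costed events per arm and adjust the interval as events accrue. Arm-specific intervals fixed in advance from the 66 and 134 should be avoided because they build in the hypothesised effect. Every 6th TPE and 13th RACD event would give 134/6 ≈ 22 and 134/13 ≈ 10 if there were none.

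The cost is a few sentences of wording and, if 10 per arm is kept, three or four more costed TPE events. No new data are needed for the definition, since household coordinates are already collected.
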